2.3 Exploratory Objectives

Exploratory objectives will assess the value of tissue biomarkers as predictors of response to pembrolizumab, including the following:

- To characterize PD-1 pathway specific expression and correlate with response
- To characterize serum biomarkers of immune, inflammatory response and other biomarkers during treatment
- To characterize levels of soluble PD-L1 related to treatment with pembrolizumab
- To characterize T-lymphocyte subset changes to treatment with pembrolizumab
- To investigate the prevalence and clinical correlation of chromosome 9p24.1 alterations for this population
- Assess cysteine-cysteine thymus and activation related chemokine (TARC) as a biomarker for response and PET normalization

Each enrolled patient will provide a fresh tissue biopsy sample if available from the biopsy performed for diagnosis, or an archived sample as agreed upon by the PI for additional marker expression analysis. Peripheral blood will be obtained at specified time points for serum marker analysis.

Initial Version date: March 10th, 2017

Amendment 6: March 29th, 2019

19

PD-1 Pathway Marker Expression

Tissue sample slides from the baseline biopsy will be evaluated by immunohistochemistry for expression of PD-1 and PD-L1 on either malignant cells or within the tumor microenvironment. Samples will be deemed either positive or negative for marker expression. Presence/absence (binary) of PD-1 and PD-L1 will be correlated with response to pembrolizumab and clinical outcomes.

Immune and Inflammatory Markers

Peripheral blood will be tested for serum levels of TNF- α , IFN- γ , IL-2, galectin-1, TGF- β , IL-10, IL-13, and indoleamine 2 3-dioxygenase (IDO). Testing will be performed using commercially available kits. Levels will be compared from specified time points through treatment.

Soluble PD-L1

Peripheral blood obtained at day 1 of cycle #1 then at the off-treatment visit will be analyzed by a commercially available ELISA assay (USCN Life Sciences – product number SEA788Hu). Levels will be compared to evaluate for a change (increase/decrease) following treatment with pembrolizumab.

Lymphocyte Subset Changes

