4.2.2 Standard Chemotherapy

4.2.2.1 Cycle 1 & 2: AVD chemotherapy post pembrolizumab "lead in" Treatment should be administered on day 1 of each 28 day cycle after all procedures/assessments have been completed as detailed

on the Study Procedures Table (Section 5.0). Trial treatment may be administered up to 3 days before or after the scheduled Day 1 of each cycle due to administrative reasons.

Doxorubicin (Adriamycin) 25 mg/m², vinblastine 6 mg/ m², and dacarbazine 375mg/ m² will be on day 1 and 15 of a four week cycle.

- All patients will receive treatment with 2 cycles of AVD.
- Treatment will commence 21 days after final dose of induction pembrolizumab, but not prior to PET #2 (+/- 3 days). Treatments will be on days 1 and 15 of a 28-day cycle.
- PET-CT (PET#3) should occur on day 117-120, or day 26-29 of AVD cycle 2 as listed in section 5.0.

AVD supportive care measures

Pre-medications:

We recommend patients receive pre-treatment with acetaminophen 650 mg po and diphenhydramine 50 mg po given 30 minutes prior to AVD as per institutional protocol.

Prophylactic antibiotics:

Prophylactic antibiotic use (e.g., Levaguin, nystatin) is at the discretion of the treating physician.

Growth factor protocol:

In elderly patients granulocyte colony stimulating factor (e.g., G-CSF) is recommended and in accordance with ASCO guidelines. Please record all granulocyte (or erythrocyte) colony stimulating factors on the treatment forms.

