4.2.2.2 Cycle 3-6: AVD (or escBEACOPP)

4.2.2.2.1 For those with a negative PET #3

For all patients with a negative PET #3, additional AVD should commence 4 weeks after day 1 cycle 2 of AVD (after PET#3). Patients will receive a total of 4-6 cycles depending on stage and tolerability.

- a. Patients with stage I/II disease should receive two additional cycles of AVD for a total of 4 cycles of AVD. Patients with bulky disease (>10 cm mass) at baseline and a negative PET #3 may receive 4-6 cycles of AVD per investigator discretion.
- b. Patients with stage III/IV disease should receive four additional cycles of AVD for a total of 6 cycles of AVD

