4.6.2 Duration of Follow Up

Once patients are off treatment for any reason, they will have a final off-treatment visit approximately 30 days post-last dose of study therapy. Thereafter, they will be followed with at least one clinic visit every 3 months for up to 2 years from end of treatment. Patients removed from treatment for unacceptable adverse events will be followed until resolution or stabilization of the adverse event.

For patients who undergo allogeneic stem cell transplant (SCT) within 2 years of study treatment, transplant parameters and adverse events will be recorded as detailed in section 4.6.3.

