5.0 STUDY PROCEDURES

Trial Period:	Screening Phase	Treatment Cycles ¹							Off Rx	Surveillance		
		Pemb	orolizun	nab		AVD ^{2,3}		AVD ^{3,4}	Assessment	Pembrolizumab ⁵	Discont	Survival Follow-Up
Treatment Cycle/Title:	Main Study Screening	1	2	3	PET #2	1-2	PET #3	3-66	emo Asses	4-35		
Scheduling Window (Days):	Within 28 days of registration	1 ± 3	22 ± 3	43 ± 3		64 ± 3		120 ± 3	Post-Chemo	2-4 weeks after last dose of chemotherapy ± 3	30 days after last dose (pembro or AVD, ±5 days)	Every 12 weeks
Administrative Procedures												
Informed Consent	X											
Inclusion/Exclusion Criteria	X											
Demographics and Medical History	x											
Prior and Concomitant Medication Review	х	X	х	x		х		Х		X	X	
Trial Treatment Administration		X	X	X		X		X		X		
Post-study anticancer therapy status											X	X
Survival Status ⁷												X
Clinical Procedures/Assessments												
Review Adverse Events		X	X	X		X		X		X	X^{20}	X^{20}
Physical Examination	X	X	X	X		X		X		X	X	
Vital Signs ⁸ Weight and Height ²⁴	X	X	X	X		X		X		X	X	
ECOG Status ⁹	X	X	X	X		X		X		X	X	
Echocardiogram/MUGA	X							X^{21}				
Unfavorable risk factors/IPS ¹⁰	X											
Laboratory Procedures/Assessments: analysis performed by LOCAL laboratory												
Pregnancy Test – Urine or Serum β-HCG	x ²²	x ²²										
PT/INR and aPTT	Х											

Trial Period:	Screening Phase	Treatment Cycles ¹							Off Rx	Surveillance		
		Pemb	orolizun	nab		AVD ^{2,3}		AVD ^{3,4}	Assessment	Pembrolizumab ⁵	Discont	Survival Follow-Up
Treatment Cycle/Title:	Main Study Screening	1	2	3	PET #2	1-2	PET #3	3-6 ⁶		4-35		
Scheduling Window (Days):	Within 28 days of registration	1 ± 3	22 ± 3	43 ± 3		64 ± 3		120 ± 3	Post-Chemo	2-4 weeks after last dose of chemotherapy ± 3	30 days after last dose (pembro or AVD, ±5 days)	Every 12 weeks
CBC with ANC ¹¹	x ¹¹	X	X	X		x^3		\mathbf{x}^3		X	X	
Comprehensive Serum Chemistry Panel ¹¹	x ¹¹	X	Х	х		x^3		x^3		х	X	
Urinalysis	X											
T3, FT4 and TSH ¹²	X			Х						X		
ESR	X											
HIV, Hepatitis B, Hepatitis C ¹³	X											
Quantiferon-gold TB blood test ²⁵	x ²⁵											
Efficacy Measurements												
PET-CT ¹⁴	x ¹⁴				x ¹⁴		x ¹⁴		X ¹⁵	x ¹⁶	x ¹⁵	
CT scan ¹⁷	X									x ²³	X	
Tumor Biopsies/Archival Tissue Collection/Correlative Studies Blood performed by CENTRAL laboratory												
Archival or Newly Obtained Tissue Collection ¹⁸	X		x ¹⁸									
Correlative Studies Blood Collection ¹⁹		х				х					x	

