- ¹⁴ PET/CT is required for eligibility within 6 weeks prior to registration (standard of care) and at specified time points for tumor assessment for the primary endpoint analysis. PET#2 should take place prior to starting AVD (research procedure). PET#3 should take place at the end of AVD Cycle 2 (standard of care). Copies of PET/CT scans should be de-identified and CD disks with DICOM files shipped within 30 days for central review as outlined in section 6.3.1.
- ¹⁵ All patients will have a PET/CT 2-6 weeks after the completion of chemotherapy (or diagnostic CT's for patients with Stage I/II disease and a negative PET#3) (standard of care). This will be prior to starting consolidation treatment (when applicable) or as part of the procedures for study discontinuation. Patients receiving consolidation will also have a final PET/CT as part of study discontinuation.
- ¹⁶ For patients who receive pembrolizumab consolidation, imaging is recommended every 3 months. Once a PET-CT is negative, patients may undergo CT's every three months during consolidation.
- ¹⁷ Diagnostic quality CT scan of the chest/abdomen/pelvis is required within 6 weeks prior to registration. If there is involvement of the neck then a diagnostic quality CT Neck is required.
- ¹⁸ Correlative studies on tissue specimens are recommended if there is adequate tissue on the baseline sample acquired for diagnosis. Patients who agree to undergo a repeat biopsy (optional: done as a research procedure) for the interim assessment will provide tissue 2-4 weeks after the first dose of pembrolizumab as specified in the lab manual, however repeat biopsy is not required.
- ¹⁹ See separate lab manual for details of correlative studies (research procedures). Study labs include:
 - (1) sodium heparin tube for FlowCore,
 - (2) SST tube for Inflammatory and Immune Markers,
 - (3) SST tube for Soluble PD-L1
 - (4) SST for CCL17

¹ Treatment cycle of pembrolizumab defined as 21 days, Treatment cycle of AVD defined as 28 days with treatment on days 1 and 15

² Interim assessment by FDG-PET #2 for primary endpoint assessment on day 64 +/- 3 days

³Labs including CBC w/ANC and comprehensive chemistry panel, physician visit with physical examination and vital signs to be performed on day 1 of each cycle of AVD.

⁴ Interim assessment by FDG-PET #3 for PET-directed therapy on day 117-120 prior to AVD cycle 3

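### Soluble PD-L1 is compared only between cycle 1 day 1 and the off-treatment visit, so a change cannot be separated from later chemotherapy or consolidation; the scheduled start-of-AVD draw goes unused

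*Combined protocol and SAP*

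**What the plan says.** The exploratory objective in section 2.3 is "To characterize levels of soluble PD-L1 related to treatment with pembrolizumab". The paragraph on this marker names two time points: "Peripheral blood obtained at day 1 of cycle #1 then at the off-treatment visit will be analyzed". It gives the purpose as follows: "Levels will be compared to evaluate for a change (increase/decrease) following treatment with pembrolizumab".

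Section 4.6.2 sets the second time point. Once off treatment for any reason, "they will have a final off-treatment visit approximately 30 days post-last dose of study therapy". The schedule in section 5.0 counts the 30 days from the last pembrolizumab or AVD dose.

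Section 4.2.2.1 puts chemotherapy between the two samples: "All patients will receive treatment with 2 cycles of AVD". For patients with a negative PET#3, section 4.2.2.2.1 adds: "Patients will receive a total of 4-6 cycles depending on stage and tolerability".

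The section 5.0 row "Correlative Studies Blood Collection" is marked in three columns: pembrolizumab cycle 1, AVD cycles 1-2 (day 64 ± 3) and discontinuation. Footnote 19 lists the tubes for that draw, including "3) SST tube for Soluble PD-L1", and does not limit the tube to particular visits. Section 9.3.5 speaks only of specified time points. Section 10.3.3 plans baseline against post-pembrolizumab comparisons related to PET#2. It lists several blood markers, but soluble PD-L1 is not among them.

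**The concern.** The question is what pembrolizumab does to soluble PD-L1. The two samples chosen bracket the whole regimen. Between them lie three induction doses, chemotherapy, any tumour clearance that chemotherapy produces and, for some patients, a second and much longer course of pembrolizumab. A rise or fall cannot be assigned to any one of these, and there is no concurrent control group to help.

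The intervening treatment also differs between patients, and it differs by age, stage and PET#3 result. A pooled change would average over quite different exposures, and a subgroup comparison would compare treatment paths as much as biology. Section 9.0 says the role of this marker in Hodgkin lymphoma is unclear, so the usefulness of the result depends on knowing which treatment it follows.

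**Working it through.** The plan gives no sample size, effect size or test for soluble PD-L1, so there is no figure to reproduce. The check is calendar arithmetic from the protocol's own schedule, assuming no delays.

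**Inputs.** Pembrolizumab induction on days 1, 22 and 43 (section 5.0). AVD from day 64 in 28-day cycles, given on days 1 and 15 (section 4.2.2.1). Consolidation starting 4 weeks after day 1 of the final AVD cycle, then every 21 days for 14 or 32 doses (section 4.2.3). Off-treatment visit 30 days after the last dose (sections 4.6.2 and 5.0).

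**Without consolidation, c AVD cycles.**
- Last infusion day = 64 + 28(c − 1) + 14.
- Off-treatment day = last infusion day + 30.
- Days since last pembrolizumab = off-treatment day − 43.

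| AVD cycles | Infusions | Last infusion | Off-treatment sample | Days since last pembrolizumab |
|---|---|---|---|---|
| 2 | 4 | 106 | 136 | 93 |
| 4 | 8 | 162 | 192 | 149 |
| 6 | 12 | 218 | 248 | 205 |

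The 2-cycle row counts from the last AVD dose. It describes patients under 60 with a positive PET#3, who get no more AVD (section 4.1) and may move to escBEACOPP with or without radiotherapy (section 4.2.2.2.2). If escBEACOPP counts as study therapy, the visit is later.

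**With consolidation, k doses.**
- Start day = 64 + 28(c − 1) + 28.
- Last dose day = start day + 21(k − 1).
- Off-treatment day = last dose day + 30.

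Results:
- c = 4, k = 32: start 176, last dose 827, sample day 857.
- c = 6, k = 32: start 232, last dose 883, sample day 913.
- c = 5, k = 14 (5 cycles is an assumed example): start 204, last dose 477, sample day 507.

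These patients have had 35 or 17 pembrolizumab doses in total and are sampled 30 days after the last one. The others who complete induction have had 3 doses and are sampled 93 to 205 days after the last one.

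**The scheduled draw under AVD cycles 1-2.** If it is taken on AVD cycle 1 day 1 before dosing, it falls on day 64. That is 64 − 43 = 21 days after the third pembrolizumab dose, with no AVD infusions, and it coincides with PET#2 (day 64 ± 3, section 6.4.1). If it is taken on day 1 of AVD cycle 2, it falls on day 64 + 28 = 92, after two AVD infusions. The exact draw day therefore matters.

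**The sections side by side.** Section 2.3 assays two time points. Section 5.0 with footnote 19 implies three draws with a soluble PD-L1 tube. Section 10.3.3 describes the post-pembrolizumab contrast but omits this marker. The three do not agree, and only section 2.3 says which soluble PD-L1 samples are compared.

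**The case against.** The strongest reply is that the plan already points the right way. Section 10.3.3 sets out baseline against post-pembrolizumab changes, a signed rank test for change and a rank sum test against PET#2 response. It extends a similar analysis to serum cytokines, immune and inflammatory markers, lymphocyte subsets and TARC. Footnote 19 lists the soluble PD-L1 tube without restriction, and a lab manual outside these documents may settle details. On this view section 2.3 is an inconsistency to reconcile, and not a deliberate choice of a confounded contrast. That much stands: nothing in the documents shows such an intention. It does not remove the point. The only passage that names the comparison for this marker omits the post-induction sample, and which samples are compared is a protocol matter.

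A second reply is that the objective is descriptive and exploratory, with no threshold or decision attached. That also stands, and it limits the weight of the point.

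Three stronger readings might be inferred, and the documents do not support them.
- **Every patient has had 4-6 AVD cycles by the second sample.** Patients under 60 with a positive PET#3 get 2. Chemotherapy-intolerant patients may stop early, and a patient who stops during induction has had none.
- **A pre-chemotherapy sample is certainly being drawn already.** The column covers AVD cycles 1-2. The day 64 window and the rule in section 4.2.2.1 that procedures precede dosing make a pre-dose draw likely, but no passage fixes it.
- **The day 64 contrast isolates a direct drug effect.** Tumour clearance during induction remains part of it.

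**Conclusion.** The point holds as a minor one. As section 2.3 is written, the soluble PD-L1 contrast cannot separate pembrolizumab from later therapy in any patient who goes on to AVD. The second sample falls anywhere from about day 136 (2 AVD cycles, counted from the last AVD dose) to about day 913 (6 AVD cycles and 32 consolidation doses). Chemotherapy exposure, total pembrolizumab doses and time since the last dose all differ by treatment path. These days assume no delays.

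A contrast that excludes chemotherapy appears to be available from a draw already in the schedule, provided that draw is taken before the first AVD dose. The primary complete-response analysis, sample size and monitoring rules do not depend on this marker.

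**What to change.** Reconcile sections 2.3, 5.0 (footnote 19) and 10.3.3:

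- **Section 2.3:** make the main exploratory soluble PD-L1 contrast cycle 1 day 1 against AVD cycle 1 day 1.
- **Section 5.0:** state that the correlative sample in the AVD cycles 1-2 column is drawn on AVD cycle 1 day 1, before the first AVD dose, and that soluble PD-L1 is assayed on it.
- **Section 10.3.3:** name soluble PD-L1, with a signed rank test for the change and a rank sum test of the change against PET#2 response, as for the other markers.
- **Off-treatment sample:** keep it as a descriptive whole-regimen time point, tabulated by treatment received and time since the last pembrolizumab dose.

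The cost is a few sentences and at most one extra assay per patient on a tube already scheduled. The report should say that tumour clearance during induction contributes to the day 64 change.

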3.0 PATIENT ELIGIBILITY

The target population for this study is patients with Hodgkin lymphoma. This will be a multicenter trial conducted at the Robert H. Lurie Comprehensive Cancer Center of Northwestern University. Northwestern University will serve as the lead site and coordinating center for this study. Participating sites will include Rutgers Cancer Institute, Memorial Sloan Kettering Comprehensive Cancer Center, and Emory University.

A total of 26 evaluable subjects will be needed for this trial (therefore up to 30 may be enrolled in order to achieve this goal). Potential patients may be referred to the Principal Investigator (PI) at Northwestern University, [name] at [contact], or to the local PI at each participating site.

Eligibility will be evaluated by the study team according to the following criteria. Eligibility waivers are not permitted. Subjects must meet all of the inclusion and none of the exclusion criteria to be registered to the study. Study treatment may not begin until a subject is registered. Please refer to Section 11.3 for complete instructions regarding registration procedures.

3.1 Inclusion Criteria

- 3.1.1 Patients must have a histologically confirmed diagnosis of classical Hodgkin lymphoma including nodular sclerosis, mixed cellularity, lymphocytic-rich, and lymphocyte depleted subtypes by the 4th edition of the WHO Classification of Tumours of Haematopoietic and Lymphoid Tissues published in 2008 (NLPHL excluded).⁴⁵
- 3.1.2 Patients must have measurable disease by the Lugano Criteria (Appendix C).
- 3.1.3 Patients must have previously untreated disease (except for one week or less of corticosteroids).
- 3.1.4 Patients must be age ≥ 18 years.
- 3.1.5 Patients must exhibit a/an ECOG performance status of 0-1.
- 3.1.6 Stage III and IV patients may any International Prognostic Score (IPS).
- 3.1.7 Stage I and II patients must have at least one NCCN unfavorable risk factor (see Appendix D).
- 3.1.8 Patients must have adequate organ and bone marrow function within 14 days prior to registration, as defined below:

leukocytes ≥ 3,000/mcL
 absolute neutrophil count ≥ 1,500/mcL
 platelets ≥ 100,000/mcl

total bilirubin within normal institutional limits

AST(SGOT)/ALT(SPGT) ≤ 2.5 X institutional upper limit of normal (ULN)

creatinine within normal institutional limits

Platelet transfusions are acceptable prior to treatment to achieve the above numbers, however growth factors are not allowed within 14 days of registration.

3.1.9 Females of child-bearing potential (FOCBP) and males must agree to avoid becoming pregnant, or impregnating a partner, respectively, by complying with any of the approved contraception techniques (see section 4.5.2) prior to registration, for the duration of study participation, and for 120 days following completion of therapy. Abstinence is acceptable if this is the usual lifestyle and preferred contraception for the subject. Should a female patient become pregnant or suspect she is pregnant while participating in this study, she should inform her treating physician immediately.

NOTE: Male patients will be considered of non-reproductive potential if they have azoospermia. Female patients will be considered of non-reproductive potential if they are either:

- (1) post-menopausal (defined as at least 12 months with no menses without an alternative medical cause; in women < 45 years of age a high follicle stimulating hormone (FSH) level in the postmenopausal range may be used to confirm a postmenopausal state in women not using hormonal contraception or hormonal replacement therapy. In the absence of 12 months of amenorrhea, a single FSH measurement is insufficient.);
- (2) have had a hysterectomy and/or bilateral oophorectomy, bilateral salpingectomy or bilateral tubal ligation/occlusion, at least 6 weeks prior to screening;
 OR
- (3) has a congenital or acquired condition that prevents childbearing.
- 3.1.10 FOCBP must have a negative pregnancy test within 7 days prior to registration on study. NOTE: a negative pregnancy test is also required within 3 days prior to first dose of pembrolizumab and therefore may need to be repeated if screening test is more than 3 days prior to first dose.
- 3.1.11 Patients must have the ability to understand and the willingness to sign a written informed consent prior to registration on study.

3.2 Exclusion Criteria

- 3.2.1 Patients are not eligible who have had prior chemotherapy, targeted small molecule therapy, or radiation therapy prior to registration.

 NOTE: If subject received major surgery, they must have recovered adequately from the toxicity and/or complications from the intervention prior to starting therapy.
- 3.2.2 Patients who have a diagnosis of immunodeficiency or are receiving systemic steroid therapy or any other form of immunosuppressive therapy within 7 days prior to registration are not eligible.
- 3.2.3 Patients who have a known history of active TB (Bacillus Tuberculosis) are not eligible.
- 3.2.4 Patients must not have a history of allergic reactions attributed to compounds of similar chemical or biologic composition to pembrolizumab.
- 3.2.5 Patients who have an uncontrolled intercurrent illness including, but not limited to any of the following, are not eligible:
 - Symptomatic congestive heart failure (ejection fraction lower than institutional lower limit of normal [LLN]
 - Unstable angina pectoris
 - Cardiac arrhythmia
- 3.2.6 Patients who have a known additional malignancy that is progressing or requires active treatment are not eligible. NOTE: Exceptions include basal cell carcinoma of the skin or squamous cell carcinoma of the skin that has undergone potentially curative therapy or in situ cervical cancer.
- 3.2.7 Patients who have known active central nervous system (CNS) metastases and/or carcinomatous meningitis are not eligible.

NOTE: Subjects with previously treated brain metastases may participate provided they are stable (without evidence of progression by imaging for at least four weeks prior to the first dose of trial treatment and any neurologic symptoms have returned to baseline), have no evidence of new or enlarging brain metastases, and are not using steroids for at least 7 days prior to registration. This exception does not include carcinomatous meningitis which is excluded regardless of clinical stability.

- 3.2.8 Patients who have active autoimmune disease that has required systemic treatment in the past 2 years are not eligible (i.e. with use of disease modifying agents, corticosteroids or immunosuppressive drugs).

 NOTE: Replacement therapy (e.g. Thyroxine, insulin, or physiologic corticosteroid replacement therapy for adrenal or pituitary insufficiency, etc.) is not considered a form of systemic treatment.
- 3.2.9 Patients who have a history of (non-infectious) pneumonitis that required steroids or current pneumonitis are not eligible.
- 3.2.10 Patients who have an active infection requiring systemic therapy are not eligible, except for uncomplicated urinary tract infections.
- 3.2.11 Patients are not eligible who have a history or current evidence of any condition, therapy, or laboratory abnormality that might confound the results of the trial, interfere with the subject's participation for the full duration of the trial, or is not in the best interest of the subject to participate, in the opinion of the treating investigator.
- 3.2.12 Patients who have known psychiatric or substance abuse disorders that would interfere with cooperation with the requirements of the trial are not eligible.
- 3.2.13 Patients may not be pregnant or breastfeeding, or expecting to conceive or father children within the projected duration of the trial, from registration through 120 days after the last dose of trial treatment.
- 3.2.14 Patients who have received prior therapy with an anti-PD-1, anti-PD-L1, or anti-PD-L2 agent are not eligible.
- 3.2.15 Patients who have a known history of Human Immunodeficiency Virus (HIV) (HIV 1/2 antibodies) are not eligible.
- 3.2.16 Patients who have active Hepatitis B (e.g., HbsAg reactive) or Hepatitis C (e.g., HCV RNA [qualitative] is detected) are not eligible.
- 3.2.17 Patients who received a live vaccine within 30 days of planned start of study therapy are not eligible. Examples of live vaccines include, but are not limited to, the following: measles, mumps, rubella, varicella/zoster, yellow fever, rabies, BCG, and typhoid vaccine.

NOTE: Seasonal influenza vaccines for injection are generally inactivated flu vaccines and are allowed; however intranasal influenza vaccines (e.g., Flu-Mist®) are live attenuated vaccines, and are not allowed.

